5.0 METHODOLOGY

5.1 Patient Admission Criteria (Diagnosis / Medical Table)

Symptoms such as fever, weakness, cough, mild shortness of breath between the ages of 40-75 referring to the clinic with COVID-19 (SARS-CoV-2) test positive or atypical in CT findings. Patients with signs of pneumonia and considered COVID 19, undergoing intubation treatment in the intensive care unit, and meeting the inclusion / exclusion criteria. Patients who are not found suitable according to the intervals specified in the Inclusion / Exclusion criteria will not be included in the study.

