5.2 Inclusion Criteria

- Respiratory rate ≥ 30

- Dyspnea and breathing difficulties findings

- Cases with oxygen saturation below 90% despite nasal oxygen support of 5 liters / minute and above

- Cases with partial oxygen pressure below 70 mmHg despite nasal oxygen support of 5 liters / minute and above

- PaO2 / FiO2 <300

Lactate> 4 *mmol* / *L*

Bilateral infiltrations or multi-lobar involvement on chest x-ray or tomography

- Hypotension (systolic blood pressure <90 mmHg,> 40 mmHg drop from usual SKB, mean arterial pressure <65 mmHg)

- Skin perfusion disorder

Organ dysfunction such as kidney function test, liver function test disorder, thrombocytopenia, confusion

Presence of immunosuppressive disease-

Presence of uncontrolled comorbidity with more than one feature

- Troponin height, arrhythmia
- COVID 19 Test positivity

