- The patient is given 100% oxygen for 2 minutes,
- Sterile gloves are worn,
- Steerable catheter is advanced through the airway to the orotracheal region in accordance with the aseptic technique.
- Fiberoptic UVC is advanced through the line catheter in accordance with the aseptic technique.
- When the catheter inserted through the nose or mouth reaches the pharynx, the patient is coughed and the catheter is advanced in the inspiratory phase and UVC is applied.
- The patient is monitored throughout the procedure,
- After the procedure, the patient is given 100% oxygen for 1 minute.
- The time required for the tracheal application of the energy required for the microorganism inactivation with the power value applied by the UVC source, these values are indicated in the table below according to the trachea diameter. (Table 1).

Respiratory Application Diameter Mm	Power Per Unit Area	Application time	Energy Required
Diameter (mm)	mw/cm ²	S	mj/cm ²
5	67,90	2,95	200
10	61,11	3,27	200
15	57,72	3,47	200
20	55,00	3,64	200
25	52,28	3,83	200
30	49,57	4,03	200
35	46,85	4,27	200
40	44,14	4,53	200
45	42,10	4,75	200
50	40,74	4,91	200
	(Table	1)	

Depending on the trachea diameter in the drawn CT, force should be applied for the time specified in the relevant table. The amount of energy to be transferred to the tissue is arranged according to the table with each advance of the fiberoptic catheter 1 cm.

The healthcare personnel who receive the treatment, taking into consideration the clinical condition of the patient, should not exceed the maximum application time (30 min \pm 5 min in intravascular applications, 5 min \pm 1 min in intrarespiratory applications), and this should be at most 5 days. should apply in accordance with the protocol.

CLINICAL WORK TREATMENT AND FOLLOW-UP PROGRAM								
Evaluation	Screening Visit (Day 0)	Inclusion / Randomization (Day 0)	Treatment Visit (Day 1)	Treatment Visit (Day 2)	Treatment Visit (Day 3)	Treatment Visit (Day 4)	Treatment Visit - Final (Day 5)	Label Period / Follow-up Visit (Day 7&15)
Informed Volunteer Consent Form	Х							
Demographic information	X							
Medical history / General physical examination	X	X	X	X	X	X	X	x
Current treatments (drugs)	X	X	x	x	X	X	X	
Biochemistry, Complete blood count	X	X	x	x	X	X	X	x
Radiological Imaging	X	X		X			X	X
Vital findings	X	X	X	X	X	X	X	X
Include / exclude criteria		X	X	X	Х	X	X	
Pregnancy test (serum / urine)	X	X						
randomization		X						
Dose diary			X	X	X	X	X	

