5.5 Primary Endpoints

• Ending the vital functions of the patient (medically accepted ex)

Or

- Gloskow Coma Level 13 and above,
- At least 3 days body temperature must have remained normal (measurement from the ear 37.5 C)
- Respiratory symptoms should be significantly improved
- The nucleic acid test must be negative in 2 consecutive tests for the respiratory pathogen (sampling interval must be more than 24 hours)
- Obvious healing of lesions with CT
- There should be no comorbidity or complications requiring hospitalization
- Without oxygen support SaO2 should be> 93%

All of its items have been realized

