5.6 Secondary Endpoints

- Hypersensitivity
- Temporary shortness of breath
- Rarely, redness of the skin is due to heat
- Edema
- Bleeding
- Embolization
- Hematoma
- Hyperpigmentation
- Ache
- paresthesia
- Superficial thrombophlebitis
- May cause urticaria or ulcers.
- Vascular rupture and perforation
- Visible scratch
- Iatrogenic injury may damage the surrounding tissues.
- Hemothorax or pneumothorax.
- Neighboring Nerve Damage Iatrogenically
- phlebitis
- Skin Burn or discoloration

If two or more adverse effects from the above adverse effects are seen, the study is terminated.

6. Statistical Evaluation:

- According to the course of the clinical trial, if we reach the research arm (100 patients), control group (100 patients), the efficacy and safety of the treatment will be examined and an interim report will be prepared. According to the results of the interim report, the clinical trial will be terminated or the clinical trial will be continued until the number of volunteers (400 in total) mentioned above is completed.
- In this interim analysis, the patients completing the study will be evaluated considering the primary and secondary endpoints stated in the protocol and the criteria are as follows:

1-Duration in intensive care

2-Survival rate

Contribution of UVC and laser beam application to the treatment of 3-COVID 19 infection and / or superinfections accompanying COVID 19 infection

The tests to be applied are as follows:

1-Difference test between two averages for intensive care stay

(Mann-Whitney U test or t test) will be used.

2-Survival analysis tests will be used for survival rate.

Accompanying 3-COVID 19 infection treatment and / or COVID 19 infection

To investigate the contribution of UVC and laser beam application to the treatment of superinfections

Chi-square test will be applied.

Descriptive statistics will also be given for demographic data.

REFERENCE STUDIES ABOUT THE APPLICATION OF UVC BEAM "in vitro, in vivo and ex vivo"

1. The Effect of UV-C Ray Reducing Pathogen Rate on Blood Platelets Apps;

Auto-immune diseases HIV 1 -2
T-lymphotropic virus types 1 and 2
Hepatitis B (HBV)
Hepatitis C (HCV)
Hepatitis A and E
Blood pathogens (Treponema pallidum)
Parvovirus B19

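### The inclusion/exclusion check is repeated on Days 1–5 after randomisation with no stated consequence, and the only stated analysis set is completers

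*Combined protocol and SAP*

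**What the plan says.** All references are to the combined protocol and SAP.

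- **Schedule, Section 5.4.1.** Randomisation is marked once, on Day 0. The row "Include / exclude criteria" is marked at that visit and at all five treatment visits, Days 1–5. The screening and follow-up cells are blank. No footnote or text explains the Day 1–5 marks.
- **Section 5.1.** The consequence of failing the criteria is given as: "Patients who are not found suitable according to the intervals specified in the Inclusion / Exclusion criteria will not be included in the study". The section concerns patient admission.
- **Section 5.2.** Many inclusion items are acute findings: respiratory rate of at least 30, PaO2/FiO2 below 300, lactate above 4 mmol/L, and "Cases with oxygen saturation below 90% despite nasal oxygen support of 5 liters / minute and above". The list ends with "COVID 19 Test positivity". It does not say whether any one item or all items are required.
- **Section 5.5.** The primary endpoint is death, or recovery on every item of a list. That list includes SaO2 above 93% without oxygen, and "The nucleic acid test must be negative in 2 consecutive tests for the respiratory pathogen".
- **Section 6.** For the interim analysis, "the patients completing the study will be evaluated". No intention-to-treat set, missing-data rule or withdrawal rule appears anywhere.

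**The concern.** Eligibility should be settled before randomisation. When it is listed again afterwards, a site can reasonably ask what to do with a patient who no longer qualifies, and here the protocol gives no answer. Several criteria are of the kind that a recovering patient stops meeting, so any withdrawal prompted by the re-check would depend on how the patient responded. An analysis limited to completers would then leave those patients out.

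At stake is the protection that randomisation gives. Deaths would be counted while some survivors were not, and the share left out could differ between arms because of the treatment. Intensive care stay could suffer in the same way, since patients who improve early may be those with short stays.

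**Working it through.** The plan states no figure on this point, so there is nothing to reproduce. The check has two parts.

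**1. The passages side by side**

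| Entry criterion (5.2) | Recovery criterion (5.5) | Measured again after Day 0? |
|---|---|---|
| Positive COVID-19 test | Two consecutive negative nucleic acid tests | PCR on Days 1, 3, 5 and at follow-up |
| Saturation below 90% on at least 5 L/min oxygen | SaO2 above 93% without oxygen | Vital findings at every visit |

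A patient moving towards the recovery endpoint is therefore moving away from these entry criteria. The schedule supplies the repeated check, and Section 6 supplies an analysis set that a withdrawn patient would fall outside. The missing link is any statement that a failed re-check leads to withdrawal. The documents contain none.

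**2. What withdrawal would do, if it happened**

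Let *m* be true mortality in an arm and *q* the share of its survivors removed. Assume that no patient who dies is removed. Mortality among those kept is

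m / [m + (1 − m)(1 − q)].

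The documents give neither *m* nor *q*, so every input below is an assumption.

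Assumed true mortality 30% test v 40% control, a difference of 10 points:

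- *Removal 30% test, 15% control.* Test: 0.30 / (0.30 + 0.70 × 0.70) = 0.30 / 0.79 = 38.0%. Control: 0.40 / (0.40 + 0.60 × 0.85) = 0.40 / 0.91 = 44.0%. Difference 6.0 points.
- *Removal 15% test, 30% control.* Test: 0.30 / (0.30 + 0.70 × 0.85) = 0.30 / 0.895 = 33.5%. Control: 0.40 / (0.40 + 0.60 × 0.70) = 0.40 / 0.82 = 48.8%. Difference 15.3 points.

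Assumed true mortality 30% test v 50% control, a difference of 20 points:

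| Survivors removed, test / control | Observed test | Observed control | Difference |
|---|---|---|---|
| 20% / 20% | 34.9% | 55.6% | 20.7 points |
| 40% / 40% | 41.7% | 62.5% | 20.8 points |
| 40% / 20% | 41.7% | 55.6% | 13.9 points |

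Equal removal barely changes the difference, although it inflates both rates. With no true effect and equal removal, the two arms have the same *m* and *q*, so the difference is exactly zero. For example, 50% mortality with 20% of survivors removed gives 0.50 / (0.50 + 0.50 × 0.80) = 55.6% in both arms. The distortion comes from unequal removal.

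The formula treats survival as a crude proportion. Section 6 names survival analysis for this outcome, where a withdrawn patient would more likely be censored. Such censoring would be informative and could also bias the result, but by an amount that this formula does not give.

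**The case against.** The strongest reply is that removal of improved patients is not in the protocol. Section 5.1 governs entry and is silent about patients already randomised. The completer wording belongs to the interim analysis and does not define completion by continued eligibility. The schedule row is a bare label.

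Other text points the other way. Section 5.5 makes recovery part of the primary endpoint, which could hardly be observed if patients left on improving. The note after the schedule plans serum sampling on Days 7 and 15 following clinical improvement. Section 5.2 also includes items that would not normally resolve in five days, such as immunosuppressive disease and uncontrolled comorbidity. If one item is enough, losing a single severity value does not end eligibility.

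All of this stands. A reader might infer from the row, the admission rule and the completer wording together that improved patients will be dropped; the documents do not say so.

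A benign reading, that the marks are a daily check of the exclusions, is possible but not well supported. The exclusions in Section 5.3 (such as age under 40, a history of anaphylaxis and known DNA repair deficiency) are nearly all fixed over five days. Pregnancy testing is scheduled only at screening and Day 0. Vital signs, biochemistry and adverse events already have their own rows. The purpose of the marks remains unexplained, and no rule keeps every randomised patient in the analysis.

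**Conclusion.** The point holds as a gap with a conditional risk. Eligibility is listed again on Days 1–5 after randomisation with no purpose or consequence stated, and the only analysis population named is completers. If a failed re-check led to withdrawal, patients would be selected on response after randomisation.

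Under the assumed rates, heavier removal of test-arm survivors (30% v 15%) cuts a 10-point mortality difference to about 6 points. The opposite imbalance raises it to about 15. The direction is not fixed: more improvement in one arm would remove more of that arm's survivors, and because no blinding is described, discretionary removal could go either way.

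Two stronger readings are not supported:

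- *That the re-check would produce a false difference when treatment does nothing.* This needs unequal removal for some reason other than treatment effect, and the documents give no basis for assuming it. Equal removal gives no difference.
- *That a real benefit would be turned into apparent harm.* In the 30% v 40% example with 15% of control survivors removed, the arms become equal only when 1 − q = (0.30 × 0.91 / 0.40 − 0.30) / 0.70 = 0.546. More than about 45% of test survivors would have to be removed, and nothing in the documents suggests that.

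**What to change.** 1. In Section 6, replace the completer wording with an analysis of all randomised patients in the arm to which they were assigned, at the interim and the final analysis.
2. State that eligibility is fixed at Day 0 and that a later change in any criterion does not end follow-up or remove a patient from the analysis.
3. In the schedule, limit the inclusion/exclusion row to before randomisation. Alternatively, relabel the Day 1–5 marks as a separate check, state its purpose, and say that it has no effect on follow-up or the analysis set.

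The cost is one table edit and two sentences, with no added patients, visits or measurements. If the sponsor never intended removal, the change only writes down what was meant.

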1.0 SUMMARY of INVESTIGATION

Study Title:	Prospective, Parallel, Multicenter Randomized Controlled Study Investigating the Effects of UVC Beam and Laser Beam Therapy According to Standard Therapy in Patients with Covid-19 Diagnosis
Study Code:	MD2020/001
Device :	Turkishbeam Model Number: 1007-001
	*: The device was produced by RD GLOBAL ARASTIRMA GELISTIRME SAĞLIK ILAÇ INSAAT YATIRIMLARI A.S.
Device Classification:	Class III
Purpose of the Study:	Clinical research study that evaluates the effect of Turkish Beam- Selective UV developed by RD GLOBAL ARASTIRMA GELISTIRME SAĞLIK ILAÇ INSAAT YATIRIMLARI A.S. use into Intravascular, Intrapulmonary, Intratracial, Intrarespiratory area. Bacteria, Fungal and Virus-based pathogens systematically to collect and evaluate specific clinical performance and safety data. In our Clinical Research, we aimed to investigate the effectiveness of the treatment group and control group mortality rates, intensive care hospitalization times, monitoring the virus load by PCR, and the treatment effectiveness of UVC

Scope of the Study:	This Clinical Research covers determining the treatment effectiveness and reliability of UVC application to patient groups, the details of which are determined in the protocol.
Application:	Intravascular, Intrapulmonary, Intratracial, Intrarespiratory UVC and Laser Therapy System
Overall Study Design:	Prospective, Parellel, Multicenter, Randomized Controlled
Number of volunteers:	50 patient- 2 groups with 25 (two hundred) patients in each group
Treatment Groups:	Test: Antiviral + Antimalarial + Antibiotic Treatment + UVC Therapy Control: Antiviral + Antimalarial + Antibiotic Treatment
Groups of Volunteer:	Those who are between the ages of 40-75 and who have applied to the clinic with symptoms such as fever, weakness, cough, and shortness of breath, or who have signs of COVID-19 (SARS- CoV-2) test positive or atypical pneumonia findings in CT findings and accepted as COVID 19 infection, and patients undergoing intubation treatment in intensive care unit
Sensitive population / Vulnerable subjects:	The study will not include under-40, pregnant women and those with suspected pregnancy, previously diagnosed with mental disorders, puerperant women and lactating women

Duration of the clinical trial: 3 months (04.2020- 07.2020)

Researched Medical Condition:

and Disease

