4.0 INFORMATION ABOUT STUDY

Mechanism of Action

Ultraviolet (UV) irradiation is electromagnetic irradiation with a wavelength (100-400 nm) shorter than visible light (400-700 nm) but longer than x-rays (<100 nm). UV irradiation is divided into four separate spectral areas, including vacuum UV (100-200 nm), UVC (200-280 nm), UVB (280-315 nm) and UVA (315-400 nm). The mechanism of UVC inactivation of microorganisms is to damage the genetic material in the nucleus of the cell or nucleic acids in the virus. The UVC spectrum, especially the 250-270 nm range, is strongly absorbed by the nucleic acids of a microorganism and is therefore the inactivation wavelength range for microorganisms. This range, with a peak antimicrobial wavelength of

254nm, is known as the antimicrobial spectrum. Light-induced damage to the DNA or RNA of a microorganism usually results from dimerization of pyrimidine molecules. In particular, thymine (found only in DNA) produces cyclobutane dimers. When thymine molecules are dimerized, it becomes very difficult for nucleic acids to multiply, and if replication occurs, it often produces damage that prevents the viability of the microorganism. [1].

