Adverse Event		X	X	X	X	X	X	X
Concomitant Therapy (UVC)			x	x	x	X	x	x
PCR sampling			X		X		X	X
Serum Antibody Level			1					X

Following the improvement of the clinical course of the patients, it is planned to take the patient's serum plasma on the 7th and 15th days, and to test and store it under suitable conditions for the antibody test.

Blood tests to be performed: Complete blood count, urea, creatinine, sodium, IL-1 β , IL-6, TNF α , TGF β potassium, chlorine, AST, ALT, total bilirubin, LDH, CPK, D-dimer, troponin, Ferritin, fibrinogen, procalcitonin, CRP values, quantitative measurement of PCR results of the source of infection

Radiological Imaging: Chest X-ray and / or Lung CT is taken. Clinical decision should be made according to history and examination findings in patients who cannot have chest X-ray and / or lung CT. (Radiological findings: Consolidation, ground glass appearance and reticulo-nodular opacity

appearance should be investigated in lung CT. Signs of pneumonia in lung graphy should be examined.)

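### The visit schedule does not secure a pre-treatment PCR viral load, and on UVC days it leaves the order of sampling and irradiation open

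*Combined protocol and SAP*

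**What the plan says.** Section 1.0 (Purpose of the Study) lists among the aims "monitoring the virus load by PCR, and the treatment effectiveness of UVC". Section 5.5 makes PCR one of the recovery items: "The nucleic acid test must be negative in 2 consecutive tests for the respiratory pathogen (sampling interval must be more than 24 hours" is the stated rule. All the recovery items must be met together.

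The treatment and follow-up table in section 5.4.1 has a dedicated PCR sampling row. It is marked on Days 1, 3 and 5 and in the combined Day 7 and 15 column. The screening and randomisation columns, both Day 0, are empty. The row "Concomitant Therapy (UVC") is marked on every day from 1 to 5 and again in the Day 7 and 15 column. The text just before the table limits application to five days.

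The blood-test list below the table includes "quantitative measurement of PCR results of the source of infection", without a day, a specimen or a time relative to UVC. Section 5.2 lists "COVID 19 Test positivity" among the inclusion criteria. Sections 1.0 and 5.1 accept CT findings as an alternative to a positive test.

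Section 4.0 says that the germicidal UVC range "is strongly absorbed by the nucleic acids of a microorganism" and that UVC acts by damaging genetic material. Section 5.4.1 gives UVC to the research arm only, by both the intravascular and the airway routes. No sham procedure is described for controls.

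**The concern.** A trial that sets out to monitor viral load needs a value taken before treatment in both arms. It also needs later samples taken under the same conditions in both arms. The schedule as written secures neither. A site that follows the table exactly can take its first PCR sample after the first irradiation, and no statement on sampling order tells it otherwise.

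Two things are at stake. First, without a Day 0 value nobody can check whether the arms began with similar viral loads. Nor can anyone identify patients admitted on CT findings who were PCR-negative from the start; such patients could meet the two-negative item without clearing anything. Second, a one-arm procedure that acts on the molecule the test detects, at or near the place that may be sampled, can shift the measurement itself. Randomisation does not protect against that, because it arises after allocation and only in one arm.

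**Working it through.** No sample-size, power or error-rate figure bears on this point, so there is nothing of the plan's to reproduce. The check sets the table rows side by side and then lists the sample pairs that can satisfy the two-negative rule.

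**1. Schedule rows (section 5.4.1 table)**

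| Row | Day 0 screening | Day 0 randomisation | 1 | 2 | 3 | 4 | 5 | 7 and 15 |
|---|---|---|---|---|---|---|---|---|
| PCR sampling | – | – | X | – | X | unclear | X | X |
| UVC | – | – | X | X | X | X | X | X |
| Dose diary | – | – | X | X | X | X | X | – |
| Biochemistry, blood count | X | X | X | X | X | X | X | X |

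PCR marks at Day 0: 0 of 2 columns. PCR days that are also UVC days within Days 1 to 5: Days 1, 3 and 5, that is 3 of the 5 sampling days (1, 3, 5, 7, 15). The unclear Day 4 cell does not touch the Day 0 reading; if it were a mark, it would add another UVC-day sample.

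**2. Order and site.** The intravascular, intratracheal and orotracheal/nasotracheal steps, the table, the blood-test list and section 5.5 were read for any statement of sampling before or after irradiation, of the interval between them, or of the respiratory site. There is none.

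**3. Pairs of consecutive scheduled tests.** The nominal gaps are 3 − 1 = 2 days, 5 − 3 = 2 days, 7 − 5 = 2 days and 15 − 7 = 8 days, all longer than 24 hours.

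- Days 1 and 3: both on UVC days.
- Days 3 and 5: both on UVC days.
- Days 5 and 7: one on a UVC day for certain.
- Days 7 and 15: off treatment only if the five-day limit governs and the UVC mark in that column does not.

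So 2 of the 4 pairs lie wholly on treatment days, and the PCR item of section 5.5 can be met from those alone. The dose diary row stops at Day 5 while the UVC row does not, so the table does not settle whether the last pair is off treatment.

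**4. Possible substitute baselines**

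- *Entry test positivity (section 5.2):* undated, not quantitative, and replaceable by CT findings (section 5.1).
- *Quantitative PCR in the blood-test list:* the biochemistry row is marked at Day 0, so a Day 0 PCR might be read into it. But PCR has its own row, which omits Day 0, and a PCR on blood would not be a baseline for the respiratory-pathogen test in section 5.5.

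Neither guarantees a quantitative respiratory value before irradiation.

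**The case against.** Several points on the other side stand.

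- **Pre-treatment results will often exist.** The guideline text reproduced in section 4.6 has a respiratory sample taken on admission, and the blood-test list is ambiguous. It would therefore be wrong to infer that no patient can have an earlier PCR or that Day 1 is the only conceivable baseline. What stands is that the schedule does not require a dated, quantitative respiratory value.
- **The artefact is an inference.** Section 4.0 describes damage that prevents replication; it does not say that PCR will read low. Its specific example, thymine, occurs only in DNA, and this is an RNA virus, although the same section also names RNA damage in general. If the sample comes from the upper airway while UVC is delivered through the endotracheal tube, the sampled site may not be irradiated. A reader might want to put a figure on false negatives in the UVC arm. No passage informs such a figure, so none is given.
- **False recoveries do not follow.** A reader might infer that spurious negatives on Days 3 and 5 would create recoveries in the UVC arm. Section 5.5 also requires consciousness, temperature, symptom, CT, complication and oxygenation items, all together. PCR negativity cannot produce a recovery alone.
- **No change-from-baseline analysis is planned.** Section 6 names ICU stay, survival and a chi-square test on the contribution of UVC. A randomised comparison of later values does not need a baseline to be unbiased, so bias in a planned change analysis cannot be claimed. The difference in sampling conditions between arms remains, because it affects the later values themselves.

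**Conclusion.** The point holds in limited form. The schedule does not secure a pre-treatment viral load in either arm. All PCR samples up to Day 5 fall on UVC days, with neither order nor site stated. By the protocol's own account of mechanism and route, a sample taken soon after irradiation could read low in the research arm only.

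In countable terms: 0 of 2 Day 0 columns carry a PCR mark, 3 of 5 sampling days are UVC days within Days 1 to 5, and 2 of 4 consecutive pairs lie wholly on treatment days. The size of any measurement effect is unknown. The conclusion about differential measurement assumes that some samples are taken after irradiation, from a site the light has reached; the documents neither require nor prevent this. The missing baseline needs no such assumption.

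The main harm is to the viral-load aim and to any comparison that uses PCR. The recovery endpoint is affected only through one of its several joint items, and survival and ICU stay do not depend on PCR sampling. The defect cannot be repaired once samples have been taken, so it should be corrected before enrolment.

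**What to change.** 1. In the section 5.4.1 table, move the Day 1 PCR mark to Day 0, before randomisation, and name it as the quantitative respiratory baseline for both arms.
2. Add a sentence: every PCR sample on a UVC day is taken before that day's application, from the same named respiratory site in both arms, with controls sampled at a matching time.
3. State whether the quantitative PCR in the blood-test list is this respiratory test or a separate blood test, and on which days it is done.
4. Reconcile the UVC mark in the Day 7 and 15 column with the five-day limit, so that it is clear which samples are off treatment. Which of the two is correct is for the sponsor to settle.

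The cost is one mark moved and a few sentences, with no additional test. Sampling must be coordinated with the procedure, and the Day 1 value is given up. Sampling before that day's application fixes the order, but the Day 3 and Day 5 samples would still follow earlier days' irradiation, so a longer-lasting effect on the assay would not be excluded.
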